Up to approximately 20 subjects will be enrolled to Arm A to assess an intrasubject dose escalation schedule for CC-122.

If $> 20\%$ (eg, > 4 of 20) of subjects meet the criteria for DLT within 28 days of initial escalation to a dose level, no further intrasubject dose escalation to that dose level will be permitted.

Early DLT Evaluation for Fixed-Dose Cohorts in Arms B and C:

An initial 3 subjects will be enrolled to each of the fixed-dose escalation cohorts in Arms B and C. A dose level will be considered tolerable if 0 of 3 treated subjects experiences a DLT during the DLT evaluation period of each respective group. If 1 of 3 subjects experiences a DLT, 3 additional subjects will be enrolled to that dose level. A dose will be considered the NTD when ≥ 2 out of 6 evaluable subjects in a cohort experience a DLT. If DLTs are observed in ≥ 2 out of

6 evaluable subjects at the first dose level, a lower dose combination may be explored after review of safety data by the SRC (see Section 8.2.1).

After full enrollment and completion of the DLT evaluation period of each dose level, the number and type of DLTs and AEs occurring during the DLT evaluation period will be evaluated. A dose level will be considered tolerated after discussion of these data by the SRC. Subsequent dose cohorts will only be authorized to open for enrollment following a consensus by the SRC. Subjects enrolled in lower CC-122 fixed-dose cohorts will be allowed to escalate immediately to the next higher CC-122 dose level upon SRC approval of the subsequent CC-122 dose. For example, if the SRC has declared the 1.0 mg dose level tolerable and confirmed the opening of the 1.5 or 2.0 mg dose level, the subjects in the lower combination, ie, 0.5 mg CC-122 dose level may escalate to 1.0 mg. The MTD is defined as the highest dose level below the NTD with 0 or 1 of 6 DLT evaluable subjects experiencing a DLT during the specified DLT evaluation period. If only 3 subjects have been enrolled at the last dose level below the NTD, 3 additional subjects will be enrolled. A dose level will be declared the MTD when at least 6 subjects have been enrolled and < 2 subjects have experienced a DLT at that dose level.

An intermediate dose (ie, one between the NTD and the last dose level before the NTD) or additional subjects within any dose cohort may be added to determine the MTD and RP2D more precisely.

Monitoring for Late Toxicities During the Dose Escalation Phase:

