8.2.6. Definition of Maximum Tolerated Dose (MTD)

The MTD is defined as the last dose level below the NTD with ≤ 1 out of 6 DLT evaluable subjects experiencing DLT during the DLT evaluation period.

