10.3. Sample Size and Power Considerations

During the Dose Escalation Phase of the study, an intrasubject dose escalation schedule and standard “3 + 3” dose escalation design will be used to identify initial toxicities and safety of single agent CC-122 and to determine the MTD of the combination treatments. The final number of subjects needed in the Dose Escalation Phase depends on number of DLTs observed within each cohort. Non-DLT evaluable subjects withdrawn prior to completion of the DLT evaluation period due to reasons other than DLT will be replaced. After the MTD and preliminary RP2D have been determined for CC-122 in combination with ibrutinib and CC-122 in combination with obinutuzumab, 2 additional cohorts may be enrolled to further evaluate the safety and efficacy of the combination therapy in specific subject populations at the preliminary RP2D in the Expansion Phase.

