17. APPENDICES

17.1. Dose Escalation Rules

Table 8: Intrasubject Dose Escalation and Fixed-Doses Cohort Escalation Rules

Arm	No. of subjects recruited	Number of subjects that meet the criteria for DLT	NTD
Arm A ^[a]	20	> 20 %	
Arm B ^[b]	3+3	≥2	Yes
Arm C ^[b]	3+3	≥2	Yes

Notes:

^[a] Intrasubject escalation.

^[b] Fixed-doses cohort escalation.

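### The MTD is defined on 6 DLT-evaluable subjects but declared on 6 enrolled subjects, and neither document says which sentence governs

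*Protocol*

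**What the plan says.** The fixed-dose cohorts in Arms B and C follow a 3+3 scheme. In Protocol 4.1 (early DLT evaluation for these cohorts), three consecutive sentences deal with the MTD:

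- Definition: "The MTD is defined as the highest dose level below the NTD with 0 or 1 of 6 DLT evaluable subjects experiencing a DLT" in the evaluation period.
- Backfill: "If only 3 subjects have been enrolled at the last dose level below the NTD, 3 additional subjects will be enrolled".
- Declaration: "A dose level will be declared the MTD when at least 6 subjects have been enrolled", with fewer than 2 DLTs among them.

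The definition counts evaluable subjects; the other two count enrolled subjects. SAP 4.1.1 carries over all three. Protocol 8.2.6 defines the MTD again, with at most 1 of 6 "DLT evaluable subjects experiencing DLT during the DLT evaluation period", and 8.2.5 uses the same unit for the not tolerated dose (NTD). The preliminary rule for a level uses a third unit: "A dose level will be considered tolerable if 0 of 3 treated subjects experiences a DLT".

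On replacement, Protocol 10.3 and SAP 4.4 say: "Non-DLT evaluable subjects withdrawn prior to completion of the DLT evaluation period due to reasons other than DLT will be replaced". Evaluability is set out in Protocol 10.2 and SAP 5.2.2. In Arms B and C a subject must complete one CC-122 cycle and miss no more than 5 days, unless the missed doses were due to an IP-related AE or the cycle was cut short by a DLT. Protocol 8.6 gives forgotten or lost doses as examples of misses that count.

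**The concern.** A subject can be non-evaluable without being withdrawn. Someone who misses 6 or more CC-122 doses for a reason other than an IP-related AE, and then carries on, is enrolled and treated but not DLT-evaluable. No sentence requires that subject to be replaced; Protocol 4.1 says only that subjects may be added to a cohort. A level with 6 enrolled, 5 evaluable and 1 DLT therefore satisfies the declaration sentence and fails the definition.

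Determination of the NTD and MTD is a primary endpoint (Protocol 3.1), and the RP2D may not exceed the MTD (Protocol 4.1). SAP 5.2 and 11.1.2 base DLT percentages on the DLT-evaluable population. A report could therefore name an MTD beside a denominator of 4 or 5, against the protocol's own definition. The SAP has no rule for that case.

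**Working it through.** **1. The passages side by side**

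| Place | Decision | Unit counted |
|---|---|---|
| Protocol 4.1, SAP 4.1.1 | MTD defined | 6 DLT-evaluable |
| Protocol 8.2.6 | MTD defined | 6 DLT-evaluable |
| Protocol 4.1, SAP 4.1.1 | backfill below the NTD | 3 enrolled, then 3 more |
| Protocol 4.1, SAP 4.1.1 | MTD declared | 6 enrolled |
| Protocol 10.3, SAP 4.4 | replacement | non-evaluable and withdrawn |

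**2. How a subject falls into the gap.** Dosing on 5 of 7 days gives 4 × 5 = 20 scheduled CC-122 doses in 28 days. Missing at least 6 (30%) for a reason other than an IP-related AE makes the subject non-evaluable. Forgotten or lost doses are one route. Another is the major-surgery hold in Protocol Table 14, 3 to 7 days before through 3 to 7 days after. If CC-122 is held, this spans 3 + 1 + 3 = 7 to 7 + 1 + 7 = 15 days, which is 5 dosing days at the shortest and 10 or 11 at the longest. Only the longer holds exceed 5.

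**3. Size.** The documents give no error rate, power, DLT rate or non-evaluable fraction for dose escalation, so there is no stated figure to reproduce. I assume true DLT rates p of 0.20, 0.33 and 0.40. For n evaluable subjects:

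P(fewer than 2 DLTs) = (1 − p)^n + n·p·(1 − p)^(n−1)

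For example, p = 0.33 and n = 6 gives 0.67^6 + 6 × 0.33 × 0.67^5 = 0.0905 + 0.2673 = 0.358. Enumerating the 3+3 path gives the same value.

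| Evaluable n | p = 0.20 | p = 0.33 | p = 0.40 |
|---|---|---|---|
| 6 | 0.66 | 0.36 | 0.23 |
| 5 | 0.74 | 0.47 | 0.34 |
| 4 | 0.82 | 0.60 | 0.48 |

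The rows for 5 and 4 assume that non-evaluable subjects contribute no DLT. The declaration sentence counts any subject with a DLT, so these rows are upper bounds. If the non-evaluable subjects' DLT risk is between 0 and p, the chance lies between the 6-subject row and the row shown.

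**4. Allowing for how often it happens.** The rows for 5 and 4 condition on subjects already being lost. Let q be the assumed share who are non-evaluable but not withdrawn. The chance of at least one among 6 enrolled is 1 − (1 − q)^6. Averaging the formula in step 3 over the binomial number lost, at p = 0.33 and still with no DLT from those subjects, gives:

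| q | At least one of 6 | P(fewer than 2 DLTs) |
|---|---|---|
| 0 | 0 | 0.358 |
| 0.05 | 0.265 | 0.391 |
| 0.10 | 0.469 | 0.427 |
| 0.20 | 0.738 | 0.501 |

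**5. Precision.** With 1 DLT, the one-sided 95% Clopper-Pearson upper limit on the DLT rate is 58.2% for 1/6, 65.7% for 1/5 and 75.1% for 1/4.

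**The case against.** The strongest reply is that the definition is consistent wherever it appears: Protocol 4.1, Protocol 8.2.6 and SAP 4.1.1 all require 6 DLT-evaluable subjects. On that view the declaration sentence is only a further condition on timing. If the definition governs, the shortfall cannot occur. This stands as a possible reading, but neither document states it, and the declaration sentence is the one worded as the trigger. It would be wrong to infer that the plan uniformly permits an MTD on fewer than 6.

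Other limits also stand. The gap is narrow, and the documents give no frequency for it. A level counts as tolerated only after safety review committee (SRC) discussion, the SRC may add subjects, and late toxicity above 20% in the first 6 cycles places a level above the MTD regardless. The SAP already tabulates analysis populations by arm and cohort (Section 6), so a careful reader could find the evaluable count.

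Three stronger readings are not supported:

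- That a shortfall always eases the passage of a toxic dose. A partly dosed, non-evaluable subject can still have a DLT that counts under the declaration sentence.
- That SAP Table 8 repeats the fault, because its column is headed "No. of subjects recruited". That table has an NTD column and no MTD column, so it says nothing about declaring an MTD.
- That 3 treated, 2 evaluable and no DLT could become the MTD. The backfill sentence requires 3 more subjects first.

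**Conclusion.** The point holds as an internal contradiction in the rule for a primary endpoint. Read literally, the declaration sentence together with the limited replacement rule allows an MTD on 4 or 5 evaluable subjects, which 8.2.6 does not. At an assumed true DLT rate of 0.33, the chance of passing would rise from 0.36 to at most 0.47 with 5 evaluable and 0.60 with 4. If 5% to 20% of subjects are non-evaluable without withdrawing, it would rise to at most 0.39 to 0.50. These sizes rest on assumed rates and on no DLTs from non-evaluable subjects.

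A reader might infer that an MTD in this trial was in fact set on too few subjects. The documents do not show that. Nor does this call for a change before the trial can proceed: Phase 1 enrolment is closed and Phase 2 will not open, so what remains is how the MTD is reported. It is worth correcting before database lock, but is not critical.

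**What to change.** Reconcile the definition, backfill and declaration sentences in Protocol 4.1 and SAP 4.1.1 with Protocol 8.2.6, so that one counting unit applies and no reader has to choose. Rewording the replacement rule would have no operational effect now, and simply striking the word for withdrawal would leave an unworkable sentence.

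The change that matters is in the SAP, which Section 2 says will be finalised before database lock. Add to 11.1.2 that (a) the number of DLT-evaluable subjects is shown beside any reported MTD, and (b) a level that does not meet the 8.2.6 definition because it has fewer than 6 DLT-evaluable subjects is reported as MTD not established, with its evaluable count and DLTs. Settling this after lock would make a primary-endpoint conclusion post hoc.

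The cost is a few sentences and no new subjects or data. The downside is that an MTD claim may have to be withdrawn.

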4.2. Study Duration

The study is expected to last approximately 5 years and will consist of three phases: Screening, Treatment and Follow-up.

During the Screening Phase, lasting up to 28 days from the time of signing informed consent to first dose administered, subjects will undergo assessments to determine their eligibility.

Subjects who qualify for enrollment into the study will enter the Treatment Phase, during which subjects will receive IP at a predetermined dose and schedule until the underlying CLL has progressed or the subject has discontinued IP treatment for unacceptable toxicity or other reasons.

Subjects enrolled as of 05 Jul 2018 and who are receiving clinical benefit in the opinion of the treating investigator may continue to receive study treatment up to a maximum of 24 cycles of CC-122 irrespective of treatment arm.

The Follow-up Phase will begin at study treatment discontinuation.

4.3. End of Trial

The End of Trial is defined as either the date of the last visit of the last subject to complete the study, or the date of receipt of the last data point from the last subject that is required for primary, secondary and/or exploratory analysis, as prespecified in the protocol and/or the SAP, whichever is the later date.

5. TABLE OF EVENTS

Table 3: Table of Events – Arm A – CC-122 Single Agent

(As of 05 Jul 2018, enrollment of new subjects into Phase 1 has been discontinued; the procedures below apply to subjects continuing in the study.)

Tests and Observations	Screening	Cycle 1 and the first Cycle of each Dose Escalation ^b			Cycle 2 of each Dose Level ^b		Cycle 3 of each Dose Level ^{b, o}		≥Cycle 4 ^{b, p}	End of Treatment ^b	Follow-up
	≤ 28 Days Prior to Day 1 ^a	Day 1	Days 2 and 4 ± 1 Day	Days 8, 15 and 22 ± 1 Day	Day 1	Days 8, 15 and 22 ± 1 Day	Day 1	Days 8, 15 and 22 ± 1 Day			
Informed Consent	X	-	-	-	-	-	-	-	-	-	-
Demographics/Medical History	X	-	-	-	-	-	-	-	-	-	-
Physical Examination	X	X	-	-	X	-	X	-	X	X	X
██████████	X	-	-	-	-	-	-	-	-	-	-
Vital Signs	X	X	X	X	X	X	X	X	X	X	X
██████████	X	X	-	-	X	-	X	-	X	X	X
B-symptoms	X	X	-	-	X	-	X	-	X	X	X
Current Stage/Prognostic Classification	X	-	-	-	-	-	-	-	-	-	-
CBC & Differential	X	X	X	X	X	X	X	X	X	X	X
Clinical Chemistry	X	X	X	X	X	X	X	X	X	X	X
Beta-2 Microglobulin	X	-	-	-	-	-	-	-	-	-	-
C-Reactive Protein ^m	X	-	-	X	X	-	X	-	X	-	-
Coagulation	X	X	-	X	X	-	X	-	X	X	-
Urinalysis	X	X	-	-	X	-	X	-	X	X	-

Table 3: Table of Events – Arm A – CC-122 Single Agent (Continued)

	Screening ≤ 28 Days Prior to Day 1 ^a	Cycle 1 and the first Cycle of each Dose Escalation ^b			Cycle 2 of each Dose Level ^b		Cycle 3 of each Dose Level ^{b, o}		≥Cycle 4 ^{b, p}	End of Treatment ^b	Follow-up
		Screen	Day 1	Days 2 and 4 ± 1 Day	Days 8, 15 and 22 ± 1 Day	Day 1	Days 8, 15 and 22 ± 1 Day	Day 1	Days 8, 15 and 22 ± 1 Day		
Pregnancy Test as specified per PPRMP: (see Section 6.1.14)	X	X	-	X	X	-	X	-	X	X	X
CC-122 Contraceptive and Risk Counseling and Education	To be completed prior to each dispensing of IP as per PPRMP										
HBsAg, anti-HBc, & HCV RNA	X	-	-	-	-	-	-	-	-	-	-
Direct Antiglobulin Test	X	-	-	-	-	-	-	-	-	-	-
Amylase, lipase, fasting lipid profile (eg, cholesterol and triglycerides), creatine kinase, TSH, FT4, LDH, immunoglobulins and T-cell subsets (CD4+, CD8+ and NK cells)	X	X	-	-	X	-	X	-	X	X	-
Troponin-T and BNP	X	X	-	X	X	-	X	-	X	X	-
12-lead ECG	X	X	-	X	X	-	X	-	X	X	-
Ophthalmology Exam ^c	X	-	-	-	-	-	-	-	-	-	-
Cardiac ECHO or MUGA ^d	X	-	-	-	X	-	-	-	X ^d	X	-
Tumor Imaging Assessment ^e	X	-	-	-	-	-	-	-	X ^e	X ^e	-

Table 3: Table of Events – Arm A – CC-122 Single Agent (Continued)

	Screening ≤ 28 Days Prior to Day 1 ^a	Cycle 1 and the first Cycle of each Dose Escalation ^b			Cycle 2 of each Dose Level ^b		Cycle 3 of each Dose Level ^{b, o}		≥Cycle 4 ^{b, p}	End of Treatment ^b	Follow-up
	Screen	Day 1	Days 2 and 4 ± 1 Day	Days 8, 15 and 22 ± 1 Day	Day 1	Days 8, 15 and 22 ± 1 Day	Day 1	Days 8, 15 and 22 ± 1 Day			
Efficacy Response Assessment ^f	-	-	-	-	-	-	-	-	X ^f	X	-
[REDACTED]	X	-	-	-	-	-	-	-	-	-	-
Bone Marrow Aspirate/ Biopsy ^g	X	-	-	-	-	-	-	-	X ^g	-	-
Peripheral Blood for MRD Assessment ^h	X	-	-	-	-	-	-	-	X ^h	-	-
[REDACTED]	X	-	-	-	-	-	-	-	-	-	-
[REDACTED]	-	X	-	-	-	-	-	-	-	-	-
[REDACTED]	-	X	-	X ^k	X ^k	X ^k	-	X ^k	-	-	-
Dispense CC-122 ⁿ	-	X	-	-	X	-	X	-	X	-	-
Drug Accountability/Compliance	-	-	-	-	X	-	X	-	X	X	-
[REDACTED]	X	X	X	X	X	X	X	X	X	X	X
[REDACTED]	-	X	X	X	X	X	X	X	X	X	-

Table 3: Table of Events – Arm A – CC-122 Single Agent (Continued)

Please refer to Section 6 for a detailed description of Arm A procedures.

Table 4: Table of Events – Arm B – CC-122 Plus Ibrutinib

(As of 05 Jul 2018, enrollment of new subjects into Phase 1 has been discontinued; the procedures below apply to subjects continuing in the study.)

[figure not shown]
Tests and Observations	Screening	Cycle 1 ^b		Cycle 2 ^b		Cycle 3 ^b		Cycle 4 ^{b, n}		≥ Cycle 5 ^{b, o}	End of Treatment ^b	Follow-up
	≤ 28 Days Prior to Day 1 ^a	Day 1	Day 1	Days 2 and 4 ± 1 Day	Days, 8, 15 and 22 ± 1 Day	Day 1	Day 8, 15 and 22 ± 1 Day	Day 1	Days 8, 15 and 22 ± 1 Day	Day 1		28 days post IP discontinuation
Informed Consent	X	-	-	-	-	-	-	-	-	-	-	-
Demographics/Medical History	X	-	-	-	-	-	-	-	-	-	-	-
Physical Examination	X	X	X	-	-	X	-	X	-	X	X	X
CIRS Score Assessment	X	-	-	-	-	-	-	-	-	-	-	-
Vital Signs	X	X	X	X	X	X	X	X	X	X	X	X
ECOG PS	X	X	X	-	-	X	-	X	-	X	X	X
██████████	X	X	X	-	-	X	-	X	-	X	X	X
Current Stage/Prognostic Classification	X	-	-	-	-	-	-	-	-	-	-	-
CBC & Differential	X	X	X	X	X	X	X	X	X	X	X	X
Clinical Chemistry	X	X	X	X	X	X	X	X	X	X	X	X
Beta-2 Microglobulin	X	-	-	-	-	-	-	-	-	-	-	-
C-Reactive Protein ^m	X	-	-	-	X	X	-	X	-	X	-	-
Coagulation	X	X	X	-	X	X	-	X	-	X	X	-
Urinalysis	X	X	X	-	-	X	-	X	-	X	X	-
Pregnancy Test as specified per PPRMP: (see Section 6.1.14)	X	X	X	-	X	X	-	X	-	X	X	X

Table 4: Table of Events – Arm B – CC-122 Plus Ibrutinib (Continued)

	Screening ≤ 28 Days Prior to Day 1 ^a	Cycle 1 ^b	Cycle 2 ^b				Cycle 3 ^b		Cycle 4 ^{b, n}		≥ Cycle 5 ^{b, o}	End of Treatment ^b	Follow-up					
	Screen		Day 1	Day 1	Days 2 and 4 ± 1 Day	Days, 8, 15 and 22 ± 1 Day	Day 1	Day 8, 15 and 22 ± 1 Day	Day 1	Days 8, 15 and 22 ± 1 Day								
CC-122 Contraceptive and Risk Counseling and Education							To be completed prior to each dispensing of IP as per PPRMP											
HBsAg, anti-HBc, & HCV RNA	X	-	-	-	-	-	-	-	-	-	-	-	-	-				
Direct Antiglobulin Test	X	-	-	-	-	-	-	-	-	-	-	-	-	-				
Amylase, lipase, fasting lipid profile (eg, cholesterol and triglycerides), creatine kinase, TSH, FT4, LDH, immunoglobulins and T-cell subsets (CD4+, CD8+ and NK cells)	X	X	X	-	-	X	-	X	-	X	X							
Troponin-T and BNP	X	-	X	-	X	X	-	X	-	X	X							
12-lead ECG	X	X	X	-	X	X	-	X	-	X	X							
Ophthalmology Exam ^c	X	-	-	-	-	-	-	-	-	-	-							
Cardiac ECHO or MUGA ^d	X	-	-	-	-	X	-	-	-	X ^d	X							
Tumor Imaging Assessment ^e	X	-	-	-	-	-	-	-	-	X ^e	X ^e							
Efficacy Response Assessment ^f	-	-	-	-	-	-	-	-	X ^f	-	X ^f	X						
[REDACTED]	X	-	-	-	-	-	-	-	-	-	-	-	-					

Table 4: Table of Events – Arm B – CC-122 Plus Ibrutinib (Continued)

	Screening ≤ 28 Days Prior to Day 1 ^a	Cycle 1 ^b	Cycle 2 ^b			Cycle 3 ^b		Cycle 4 ^{b, n}		≥ Cycle 5 ^{b, o}	End of Treatment ^b	Follow-up
	Screen	Day 1	Day 1	Days 2 and 4 ± 1 Day	Days, 8, 15 and 22 ± 1 Day	Day 1	Day 8, 15 and 22 ± 1 Day	Day 1	Days 8, 15 and 22 ± 1 Day	Day 1		28 days post IP discontinuation
Bone Marrow Aspirate/ Biopsy ^g	X ^f	-	-	-	-	-	-	-	-	X ^g	-	-
Peripheral Blood for MRD Assessment ^h	X	-	-	-	-	-	-	-	-	X ^h	-	-
[REDACTED]	X	-	-	-	-	-	-	-	-	-	-	-
[REDACTED]	X	-	-	-	-	-	-	-	-	-	X	-
[REDACTED]	X	-	X ^j	-	X ^j	-	X ^j	X ^j	-	X ^j	-	-
[REDACTED]	-	X ^k	X ^k	-	X ^k	-	X ^k	-	-	-	-	-
Dispense Ibrutinib	-	X	X	-	-	X	-	X	-	X	-	-
Dispense CC-122	-	-	X	-	-	X	-	X	-	X	-	-
Drug Accountability/Compliance	-	-	X	-	-	X	-	X	-	X	X	-
Concomitant Medications/ Procedures	X	X	X	X	X	X	X	X	X	X	X	X
[REDACTED]	-	-	X	X	X	X	X	X	X	X	X	-
Allopurinol Administration as Tumor Lysis Prophylaxis ^l	X	X	X	X	X	-	-	-	-	-	-	-
Adverse Events	X	X	X	X	X	X	X	X	X	X	X	X
[REDACTED]	[REDACTED]	[REDACTED]	[REDACTED]	[REDACTED]	[REDACTED]	[REDACTED]	[REDACTED]	[REDACTED]	[REDACTED]	[REDACTED]	[REDACTED]	[REDACTED]

Please refer to Section 6 for a detailed description of Arm B procedures.

Table 5: Table of Events – Arm C – CC-122 Plus Obinutuzumab

(As of 05 Jul 2018, enrollment of new subjects into Phase 1 has been discontinued; the procedures below apply to subjects continuing in the study.)

Tests and Observations	Screening	Cycle 1 ^{b, p}							Cycle 2 ^b		Cycle 3 ^{b, q}		≥ Cycle 4 ^{b, r}	End of Treatment ^b	Follow-up
	≤ 28 Days Prior to Day 1 ^a	Day 1	Day 2	Day 4	Day 8 ± 1 Day	Day 9 ± 1 Day	Days 10 and 12 ± 1 Day	Days 16 and 23 ± 1 Day	Day 1	Days 8, 15 and 22 ± 1 Day	Day 1	Days 8, 15 and 22 ± 1 Day	Day 1		28 days post IP discontinuation
Informed Consent	X	-	-	-	-	-	-	-	-	-	-	-	-	-	-
Demographics/Medical History	X	-	-	-	-	-	-	-	-	-	-	-	-	-	-
Physical Examination	X	X	-	-	-	-	-	-	X	-	X	-	X	X	X
██████████	X	-	-	-	-	-	-	-	-	-	-	-	-	-	-
Vital Signs	X	X	X	X	X	X	X	X	X	X	X	X	X	X	X
██████████	X	X	-	-	-	-	-	-	X	-	X	-	X	X	X
██████████	X	X	-	-	-	-	-	-	X	-	X	-	X	X	X
Current Stage/Prognostic Classification	X	-	-	-	-	-	-	-	-	-	-	-	-	-	-
CBC & Differential	X	X	X	-	X	X	X	X	X	X	X	X	X	X	X
Clinical Chemistry	X	X	X	X	X	X	X	X	X	X	X	X	X	X	X
Beta-2 Microglobulin	X	-	-	-	-	-	-	-	-	-	-	-	-	-	-
C-Reactive Protein ⁿ	X	-	-	-	X	-	-	X	X	-	X	-	X	-	-
Coagulation	X	X	-	-	X	-	-	X	X	-	X	-	X	X	-
Urinalysis	X	X	-	-	-	-	-	-	X	-	X	-	X	X	-
Pregnancy Test as specified per PPRMP: (see Section 6.1.14)	X	X	-	-	X	-	-	X	X	-	X	-	X	X	X

Table 5: Table of Events – Arm C – CC-122 Plus Obinutuzumab (Continued)

	Screening ≤ 28 Days Prior to Day 1 ^a	Cycle 1 ^{b, p}							Cycle 2 ^b		Cycle 3 ^{b, q}		≥ Cycle 4 ^{b, r}	End of Treatment ^b	Follow-up
		Screen	Day 1	Day 2	Day 4	Day 8 ± 1 Day	Day 9 ± 1 Day	Days 10 and 12 ± 1 Day	Days 16 and 23 ± 1 Day	Day 1	Days 8, 15 and 22 ± 1 Day	Day 1	Days 8, 15 and 22 ± 1 Day	Day 1	
CC-122 Contraceptive and Risk Counseling and Education		To be completed prior to each dispensing of IP as per PPRMP													
HBsAg, anti-HBc, & HCV RNA	X	-	-	-	-	-	-	-	-	-	-	-	-	-	-
Direct Antiglobulin Test	X	-	-	-	-	-	-	-	-	-	-	-	-	-	-
Amylase, lipase, fasting lipid profile (eg, cholesterol and triglycerides), creatine kinase, TSH, FT4, LDH, immunoglobulins and T-cell subsets (CD4+, CD8+ and NK cells)	X	X	-	-	-	-	-	-	X	-	X	-	X	X	-
Troponin-T and BNP	X	X	-	-	X	-	-	X	X	-	X	-	X	X	-
12-lead ECG	X	X	-	-	-	X	-	X	X	-	X	-	X	X	-
Ophthalmology Exam ^c	X	-	-	-	-	-	-	-	-	-	-	-	-	-	-
Cardiac ECHO or MUGA ^d	X	-	-	-	-	-	-	-	X	-	-	-	X ^d	X	-
	X	-	-	-	-	-	-	-	-	-	-	-	X ^e	X ^e	-
Efficacy Response Assessment ^f	-	-	-	-	-	-	-	-	-	-	-	-	X ^f	X	-
	X	-	-	-	-	-	-	-	-	-	-	-	-	-	-

Table 5: Table of Events – Arm C – CC-122 Plus Obinutuzumab (Continued)

	Screening ≤ 28 Days Prior to Day 1 ^a	Cycle 1 ^{b, p}							Cycle 2 ^b		Cycle 3 ^{b, q}		≥ Cycle 4 ^{b, r}	End of Treatment ^b	Follow-up
	Screen	Day 1	Day 2	Day 4	Day 8 ± 1 Day	Day 9 ± 1 Day	Days 10 and 12 ± 1 Day	Days 16 and 23 ± 1 Day	Day 1	Days 8, 15 and 22 ± 1 Day	Day 1	Days 8, 15 and 22 ± 1 Day	Day 1		28 days post IP discontin- uation
Bone Marrow Aspirate/ Biopsy ^g	X	-	-	-	-	-	-	-	-	-	-	-	X ^g	-	-
Peripheral Blood for MRD Assessment ^h	X	-	-	-	-	-	-	-	-	-	-	-	X ^h	-	-
[REDACTED]	X	-	-	-	-	-	-	-	-	-	-	-	-	-	-
[REDACTED]	X	-	-	-	-	-	-	-	-	-	-	-	-	X	-
[REDACTED]	X	-	-	-	-	X ^j	-	-	X ^j	X ^j	-	X ^j	X ^j	-	-
[REDACTED]	-	-	-	-	-	X	-	X ^k	-	X ^k	-	X ^k	-	-	-
Administer Obinutuzumab ^m	-	X	X	-	X	-	-	X	X	-	X	-	X	-	-
Dispense CC-122	-	-	-	-	-	X	-	-	X	-	X	-	X	-	-
Drug Accountability/Compliance	-	-	-	-	-	-	-	-	X	-	X	-	X	X	-
[REDACTED]	X	X	X	X	X	X	X	X	X	X	X	X	X	X	X
[REDACTED]	-	X	X	X	X	X	X	X	X	X	X	X	X	X	-
[REDACTED]	X	X	X	X	X	X	X	X	-	-	-	-	-	-	-
Adverse Events	X	X	X	X	X	X	X	X	X	X	X	X	X	X	X

This figure is a 2D grayscale heatmap representing a complex, multi-peaked distribution. The distribution is highly concentrated in the center, with several distinct peaks of varying intensities. The background is dark, and the peaks are represented by lighter gray shades. The distribution is roughly rectangular in shape, with the highest intensity in the central region. The peaks are irregularly spaced and of different heights, suggesting a complex underlying process or signal. The overall pattern is a dense, central cluster with a tail extending towards the bottom right.

Please refer to Section 6 for a detailed description of Arm C procedures.

